14.7 Overall Response Rate (ORR)

ORR is the proportion of patients whose best overall response per RECIST criteria is complete response (CR) or partial response (PR).

14.8 Progression-Free Survival (PFS)

PFS is defined as the elapsed time from the date of first study treatment to the earliest date of documented disease progression or death from any cause, whichever is earlier. For patients who remain alive without progression, follow up time will be censored at the date of last disease assessment.

14.9 Overall Survival (OS)

OS is defined as the elapsed time from start of treatment to death or date of censoring. Patients alive or those lost to follow-up will be censored at the last date of contact (or last date known to be alive).

15.0 ADVERSE EVENTS

The descriptions and grading scales found in the revised NCI Common Terminology Criteria for Adverse Events (CTCAE) version 4.03 will be utilized for adverse event reporting.

15.1 Purpose

Adverse event data collection and reporting, which are required as part of every clinical trial, are done to ensure the safety of patients enrolled in the studies, as well as those who will enroll in future studies using similar agents. Adverse events are reported in a routine manner at scheduled times during a trial. Additionally, certain adverse events must be reported in an expedited manner for timelier monitoring of patient safety and care.

15.2 Adverse Event

Adverse Event (AE): Can be any unfavorable and unintended sign (e.g., an abnormal laboratory finding), symptom, or disease temporally associated with the use of a drug, medical treatment, or procedure without judgment about causality. An adverse event can arise from any use and from any route of administration, formulation, or dose including an overdose. This includes any newly occurring event or a previous condition that has increased in severity or frequency since initiation of a drug, medical treatment, or procedure.

Abnormal Findings

In any clinical assessment, a value outside the normal or reference range (such as a clinical laboratory, vital sign, or ECG) will not be reported or assessed as an AE unless that value is considered to be of clinical significance by the investigator. A value of clinical significance is one that leads to discontinuation or delay in protocol treatment, dose modification, therapeutic intervention*, or is considered to be a clinically significant new finding or change from baseline by the investigator.

*Transfusion support administered to offset clinical symptoms of anemia or thrombocytopenia will not be considered therapeutic intervention.

Signs and Symptoms

Signs/symptoms resulting from an underlying clinical diagnosis should be documented as one comprehensive AE. If no underlying clinical diagnosis can be identified, each sign/symptom should be reported as a separate independent event. (A new or worsening event resulting from an underlying clinical diagnosis or a reaction to concurrent medications should be documented as a separate independent AE unless it is within the normal range of fluctuation for that patient.)

Grade Changes/Fluctuations

AEs will be reported at the maximum grade/severity experienced for the duration of the event. Should one particular event warrant further investigation, additional details may be collected at the discretion of the Principal Investigator.

Progression of Disease

Progression of disease, if documented in accordance to standard of care, should not be reported as an AE.

Tests and Procedures

Tests and procedures should not be reported as AEs. The underlying clinical diagnosis (or sign/symptom in the event an underlying clinical diagnosis is not known) requiring testing or a procedure, should be reported as an adverse event if it meets criteria for reporting.

15.3 Serious Adverse Events (see also Appendix A)

Serious AE (SAE) means any untoward medical occurrence that occurs at any dose:

1. Results in death.

2. Is life-threatening.

The term "life-threatening" in the definition of "serious" refers to an event in which the patient was at risk of death at the time of the event; it does not refer to an event which hypothetically might have caused death if it were more severe).

3. Requires inpatient hospitalization or prolongation of present hospitalization.

Elective hospitalization to simplify protocol treatment/evaluations or to treat a baseline condition that did not worsen from baseline will not be considered an SAE.

4. Results in persistent or significant disability/incapacity.

Disability is defined as a substantial disruption of a person's ability to conduct normal life functions.

5. Is a congenital anomaly/birth defect.

6. Is a medically important event.

A medically important event may not be immediately life threatening or result in death or hospitalization but may jeopardize the patient or may require intervention to

prevent one of the other outcomes listed in the definition above, or involves suspected transmission via a medicinal product of an infectious agent. Examples of such medical events include allergic bronchospasm requiring intensive treatment in an emergency room or at home, blood dyscrasias or convulsions that do not result in inpatient hospitalization, or the development of drug dependency or drug abuse; any organism, virus, or infectious particle (e.g., prion protein transmitting Transmissible Spongiform Encephalopathy), pathogenic or nonpathogenic, is considered an infectious agent.

Additional SAE classification(s) for AEs occurring at any dose or during any use of Merck product(s):

- 1. Is a new cancer (that is not a condition of the study);**
- 2. Is associated with an overdose (whether accidental or intentional):** Any adverse event associated with an overdose is considered a serious adverse event. An overdose that is not associated with an adverse event is considered a non-serious event of clinical interest and must be reported within 24 hours.

15.4 Adverse Event Collection Period

In this protocol, adverse events include only treatment-emergent adverse events. A treatment-emergent adverse event (TEAE) is defined as any event that begins or worsens after the start of protocol treatment. All baseline-emergent adverse events, any event that begins or worsens after completion of the informed consent but prior to the start of protocol treatment, should be reported as a Baseline/Comorbid Condition.

All adverse events that occur within ≤ 30 days of the last dose of study therapy will be reported and followed until resolution. Resolution is defined as a return to baseline status or the stabilization of an event with the expectation that it will remain chronic. (Exception: If a patient begins an alternative therapy that confounds accurate assessment of AEs within ≤ 30 days of the last dose of study therapy, all adverse event collection will stop and any ongoing events will be left open.)

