hypothyroidism (7.2%), pneumonitis (2.9%), hyperthyroidism (2.2%), colitis (1.3%) and skin AEOSI (1.3% including all terms). Based on the mechanism of action of MK-3475 and similar immunomodulatory agents, the Sponsor is interested in potential irAEs, and encourages appropriate investigation of signs and symptoms suggestive of these.

Consultation with the appropriate medical specialist should be considered when investigating a possible irAE. These events can occur after the first dose to several months after the last dose of treatment. Mild irAEs are usually treated symptomatically and do not require dosing delays or discontinuation. Higher grade and persistent lower grade irAEs typically necessitate withholding or discontinuing treatment and administration of systemic steroids or other immunosuppressive agents (such as tumor necrosis factor blockers), when systemic steroids are not effective. Early recognition of irAEs and initiation of treatment are critical to reduce the risk of complications, since the majority of irAEs are reversible with the use of steroids and other immune suppressants.

Identification and Treatment of irAEs

If an irAE is suspected, a thorough evaluation should be conducted in an effort to possibly rule out neoplastic, infectious, metabolic, toxin or other etiologic causes prior to diagnosing an irAE. Serological, immunological, and histological (biopsy) data should be considered to support the diagnosis of an immune-related toxicity.

A separate document entitled Pembrolizumab Program (MK-3475) Event of Clinical Interest Guidance Document is maintained and distributed to investigational sites along with this IB and study protocols. Please refer to this guidance document in conjunction with this IB when assessing irAEs. Updates and modifications to the irAE guidance document will be made and distributed to Investigators to provide the most current information, and therefore will be independent of the IB update cycle.

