- For **Grade 2-3** total bilirubin or PT/INR, pembrolizumab should be interrupted and steroids given as above. If values don't improve within 12 weeks from date of diagnosis of grade 3 toxicity to baseline or Grade 0-1, pembrolizumab should be permanently discontinued.
- For **Grade 4** total bilirubin or PT/INR, pembrolizumab should be permanently discontinued.

Immune-Mediated Hypophysitis

Hypophysitis occurred in 2 (0.5%) of 411 patients, consisting of one Grade 2 and one Grade 4 case (0.2% each), in patients receiving KEYTRUDA in Trial 1. The time to onset was 1.7 months for the patient with Grade 4 hypophysitis and 1.3 months for the patient with Grade 2 hypophysitis. Both patients were treated with high-dose (greater than or equal to 40 mg prednisone or equivalent per day) corticosteroids followed by a corticosteroid taper and remained on a physiologic replacement dose. Monitor for signs and symptoms of hypophysitis. Administer corticosteroids for Grade 2 or greater hypophysitis. Withhold KEYTRUDA for moderate (Grade 2) hypophysitis, withhold or discontinue KEYTRUDA for severe (Grade 3) hypophysitis, and permanently discontinue KEYTRUDA for lifethreatening (Grade 4) hypophysitis.

Renal Failure and Immune-Mediated Nephritis

Nephritis occurred in 3 (0.7%) patients, consisting of one case of Grade 2 autoimmune nephritis (0.2%) and two cases of interstitial nephritis with renal failure (0.5%), one Grade 3 and one Grade 4. The time to onset of autoimmune nephritis was 11.6 months after the first dose of KEYTRUDA (5 months after the last dose) and lasted 3.2 months; this patient did not have a biopsy. Acute interstitial nephritis was confirmed by renal biopsy in two patients with Grades 3-4 renal failure. All three patients fully recovered renal function with treatment with high-dose corticosteroids (greater than or equal to 40 mg prednisone or equivalent per day) followed by a corticosteroid taper.

Monitor patients for changes in renal function. Administer corticosteroids for Grade 2 or greater nephritis. Withhold KEYTRUDA for moderate (Grade 2) nephritis, and permanently discontinue KEYTRUDA for severe (Grade 3), or life-threatening (Grade 4) nephritis.

Immune-Mediated Hyperthyroidism and Hypothyroidism

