12.5 Follow-up Evaluations

For patients without documented evidence of objective disease progression the following assessments should be performed every 12 weeks until documented disease progression, death, withdrawal of consent, or end of study, whichever occurs first. A *telephone call* to the patient and/or the patient's family may be made to evaluate the patient's status on the following:

- Post-study anticancer therapy status
- Survival status
- Following confirmed disease progression or initiation of new anti-cancer therapy, survival will be assessed (at a minimum) by telephone contact every 12 weeks (± 2 weeks)."

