- ^I Imaging studies for tumor assessment for all known sites of disease (including CT or MRI of abdomen with contrast): the same method of assessment and technique used at baseline will be used during treatment and follow-up. Imaging studies will be done every 3 cycles (**after every 9 weeks, ±9 days**) from the date of Enrollment, timed to coincide with the end of the prior treatment cycle.)
- ^J AE/SAE collections should continue for at least 90-days post EoT visit. All subjects with SAEs must be followed up for outcome. (See Section 15.0 and Appendix A for details).
- ^K Follow-up for patients without documented objective disease progression shall occur every 12 weeks (+/- 2 weeks) until documented disease progression, death, withdrawal of consent, or EoS, whichever occurs first.
- ^L Telephone call may be made to patient or patient's family to follow-up on patients' post-study anticancer therapy and survival status. **Following confirmed disease progression or initiation of new anti-cancer therapy, survival will be assessed (at a minimum) by telephone contact every 12 weeks (±2 weeks).**

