- c. Events that are more frequent than anticipated or more severe than expected must be reported to the IRB within ten (10) working days of being made known to the PI.
- d. All unanticipated deaths must be reported to the IRB within 24 hours of being made known to the PI.

C. Merck Expedited Reporting, (Events of Clinical Interest or ECIs)

- a. In addition to the mandatory MedWatch 3500A Form, the PI is also required to comply with all reporting requirements as supplied by the Investigational Drug Sponsor: Merck.
- b. Any serious adverse event, or follow up to a serious adverse event, including death due to any cause other than progression of the cancer under study that occurs to any subject from the time the consent is signed through 90 days following cessation of treatment, or the initiation of new anti-cancer therapy, whichever is earlier, whether or not related to Merck product, must be reported within 24 hours to the Sponsor and within 2 working days to Merck Global Safety.
- c. Non-serious Events of Clinical Interest will be forwarded to Merck Global Safety and will be handled in the same manner as SAEs.
- d. Additionally, any serious adverse event, considered by an investigator who is a qualified physician, to be related to Merck product that is brought to the attention of the investigator at any time outside of the time period specified in the previous paragraph also must be reported immediately to the Sponsor and to Merck.
- e. **SAE reports and any other relevant safety information are to be forwarded to the Merck Global Safety [contact]**
- f. A copy of all 15 Day Reports and Annual Progress Reports is submitted as required by FDA, European Union (EU), Pharmaceutical and Medical Devices agency (PMDA) or other local regulators. Investigators will cross reference this submission according to local regulations to the Merck Investigational Compound Number (IND, CSA, etc.) at the time of submission. Additionally investigators will submit a copy of these reports to Merck & Co., Inc. (Attn: Worldwide Product Safety; [contact]) at the time of submission to FDA.
- g. All subjects with serious adverse events must be followed up for outcome.

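### Section 15.4 and the study calendar give different adverse-event windows (30 days against at least 90), and the follow-up calls list no toxicity question, so late non-serious immune-related events may go unrecorded

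*Combined protocol and SAP*

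**What the plan says.** The rules on collecting adverse events after treatment are spread over several places.

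- Section 15.4: "All adverse events that occur within ≤ 30 days of the last dose of study therapy will be reported", with each such event followed to resolution. Collection stops sooner if a confounding alternative therapy begins inside those 30 days.
- Section 12.6, footnote J: "AE/SAE collections should continue for at least 90-days post EoT visit". The calendar marks adverse events, in parentheses and with this footnote, in the Follow-Up column.
- Appendix A, part C.b: SAEs are reportable from consent "through 90 days following cessation of treatment, or the initiation of new anti-cancer therapy, whichever is earlier". Section 12.2 agrees. Section 12.4 gives 90 days without the new-therapy cut-off.
- Appendix A, part C.c: "Non-serious Events of Clinical Interest will be forwarded to Merck Global Safety and will be handled in the same manner as SAEs". Part C.d adds that related SAEs are reportable at any later time if the investigator learns of them.
- Section 8.4.1.1: after day 30, concomitant medications are still recorded for SAEs and ECIs, which implies that ECIs are expected to be captured then.
- Sections 8.6 and 12.5 and footnote L: the 12-weekly calls cover "Post-study anticancer therapy status" and survival status. After progression or new therapy, survival is the stated minimum.

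On timing, 9.1.4 says of immune-related events: "These events can occur after the first dose to several months after the last dose of treatment". Section 10.2 repeats the point. Section 9.1.4 also describes a Grade 2 autoimmune nephritis with onset "11.6 months after the first dose of KEYTRUDA (5 months after the last dose").

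Treatment-related AEs are a primary endpoint in 3.1, but toxicity profile is a secondary endpoint in 16.1. Neither 3.1 nor 16.5 says over what period events count.

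**The concern.** A descriptive safety endpoint is only as good as its ascertainment. Here the section that defines the AE collection period and the calendar that sites work from disagree by at least 60 days (90 − 30), and the contact that could supply the later data has no toxicity item. Two sets of staff could each follow the protocol and produce different AE tables. For a drug whose immune toxicity is acknowledged to appear after dosing ends, the likely direction of error is under-counting.

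Section 17.2.2 is exposed in the same way. Its stopping guideline counts treatment-related Grade 3 or higher toxicity, with exceptions, whether or not the event is serious, and it too states no window.

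**Working it through.** **Step 1. The windows side by side.**

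| Source | Events | Length | Counted from | New-therapy rule |
|---|---|---|---|---|
| 15.4 | all AEs | 30 days | last dose | stops if a confounding therapy starts within 30 days |
| 12.6, footnote J | AEs and SAEs | at least 90 days | EoT visit | none |
| 12.2 and Appendix A C.b | SAEs | 90 days | end or cessation of treatment | stops at new anti-cancer therapy |
| 12.4 | SAEs | 90 days | end of treatment | none |
| Appendix A C.c | non-serious ECIs | as SAEs, so 90 days by implication | as SAEs | as SAEs |
| Appendix A C.d | related SAEs | no limit | not applicable | none; depends on the investigator hearing of the event |

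For non-serious AEs, the first two rows contradict each other. The anchors also differ, and the new-therapy rule takes three forms.

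**Step 2. What is captured, by type of event and time.**

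- Serious immune-related events: reportable to 90 days (or new therapy), and later if related and known to the investigator.
- Non-serious ECIs: Appendix I, which carries the ECI title, covers pneumonitis, diarrhea/colitis, type 1 diabetes, hypophysitis, thyroid, hepatic and renal events, among others. Those known to the site are reportable to about day 90. This is an expedited-reporting route to the drug supplier, and nothing in the call text prompts anyone to look for the events.
- Non-serious immune-related events not in Appendix I (for example uveitis, arthritis or myositis, which 9.1.4 names): not collected after day 30 if 15.4 governs; collected to at least day 90 if footnote J governs.
- Any new non-serious immune-related event after about day 90: outside every stated minimum.

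**Step 3. Timing of contacts.** Taking 30-day months, the nephritis onset at 5 months is 5 × 30 = 150 days after the last dose, beyond both 30 and 90 days. If the 12-week interval runs from the last dose (an assumption, since the text does not fix its start), the calls fall at 12 × 7 = 84 days and 24 × 7 = 168 days. With the ±2-week allowance in footnote K, the first falls between days 70 and 98. The calls needed to serve a 90-day window therefore already exist; what is missing is the question.

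**Step 4. Size.** The documents give no rate of first immune-related events after a given day, so the loss cannot be estimated. As illustration only, let q be the assumed share of patients with such an event after collection closes, and take the plan's 28 evaluable patients. The expected number is 28q, and the chance of at least one is 1 − (1 − q)^28.

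| Assumed q | Expected among 28 | Chance of at least one |
|---|---|---|
| 1% | 0.3 | 25% |
| 3% | 0.8 | 57% |
| 5% | 1.4 | 76% |
| 10% | 2.8 | 95% |

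**Step 5. Sensitivity of the stopping guideline to one event.** With the plan's Beta(0.4, 1.6) prior, x events in n patients give a Beta(0.4 + x, 1.6 + n − x) posterior. At n = 7, the probability that the rate exceeds 20% is 0.873 with 3 events and 0.970 with 4, against the 90% threshold. One unrecorded event can thus decide whether the guideline is met. This shows sensitivity; it is not evidence that such events will be missed.

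**The case against.** The best defense is that the protocol, read whole, collects more than 15.4 suggests. Footnote J covers AEs as well as SAEs and sets a floor, not an end. The calendar marks AEs in the same Follow-Up column as the telephone call. Non-serious ECIs are handled like SAEs, and Appendix I covers the best-known immune toxicities. Section 15.3 also makes medically important events serious without hospitalization. All of this stands, and it narrows the point.

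It also rules out several stronger readings that a reader might infer.

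- *Late immune-related events as a class drop out after day 30.* They do not. Serious events and known ECIs are covered to about day 90, and footnote J has the same standing as 15.4.
- *Comparison with the pooled reference SAE rate in 9.1.4 would be uneven.* That rate used 90 days; this trial also collects SAEs to 90 days, and 16.5 plans no such comparison.
- *The cited onset medians show loss.* For the 4.6-month median treatment duration in 9.1.4, a 30-day window reaches about 4.6 + 1 = 5.6 months, past the 5-month pneumonitis median. A 90-day window reaches about 4.6 + 3 = 7.6 months, past the 6.5-month colitis median. The onset medians come from 411 melanoma patients and the treatment duration from a different pool of 2,117, and those events may have arisen on treatment.
- *The 26-day half-life implies late toxicity.* The documents do not link residual concentration to the onset of immune-related events.

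The only dated case beyond 90 days is one nephritis, reported as 0.2%; at that rate 0.002 × 28 = 0.056 would be expected here. One case does not establish an overall late rate, but it gives no ground for claiming a large one.

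The defense does not remove the contradiction between 15.4 and footnote J, supply a means of collecting AEs during follow-up, or give the endpoint a window.

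**Conclusion.** The point holds as an inconsistency with a limited ascertainment gap. Two windows apply to non-serious AEs, the follow-up calls have no AE item, and the safety endpoint has no stated period. If sites follow 15.4 and the call text, new non-serious treatment-related events after day 30 are not reliably captured, except ECIs already known to the site up to about day 90. New non-serious immune-related events after about day 90 are outside every stated minimum, whichever passage governs.

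The expected direction is an under-count; its size is unknown, and the percentages in Step 4 rest on assumed rates. The reading that non-serious ECIs have a 90-day window is an inference from Appendix A. The conclusion does not depend on whether safety is primary (3.1) or secondary (16.1), though that label should be settled too. This should be corrected; it does not undermine the efficacy design.

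**What to change.** 1. Reconcile 15.4, footnote J, 12.2, 12.4 and Appendix A to one AE and immune-related-event window, with one anchor and one new-therapy rule, no shorter than footnote J's 90-day minimum.
2. State that window for the safety endpoint in 3.1 and 16.5, and give safety the same rank in 3.1 and 16.1.
3. Add a question on suspected immune-related events to the scheduled 12-weekly calls in 8.6, 12.5 and footnote L, so that the follow-up mark in the calendar has a means of collection.
4. In 16.5, tabulate immune-related events by onset: on treatment, 0–30 days after the last dose, and more than 30 days after it. Flag those arising after new anti-cancer therapy, using the therapy status the calls already record.

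Extending collection past 90 days through the second call (about day 168) is optional. It would reach the 5-month case that the protocol cites, but nothing in the documents fixes that cut-off.

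The cost is an amendment to wording, one question on existing calls and slightly more data entry. Some late events will be confounded by later therapy, which the flag makes visible. The change concerns data collection and reporting only; it leaves dosing, toxicity management and the visit schedule as they are.
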